## NORIG Trial Protocol

### 5. Trial protocol

---

#### 5.1 Visit schedule overview

The patient-related activities of the NORIG trial can be divided into 4 phases:

- Screening for eligibility (2 visits over a maximum of 16 weeks)
- Randomization to treatment (1 visit and it may be combined with the last screening visit)
- Treatment phase (5 visits over 15 weeks)
- Treatment tapering phase (from week 15 to 17 after randomization, last week without study medication, final visit at 18 weeks)

The visit and data collection schedule described below in detail is summarized in Appendix 9.2.

#### 5.2 Screening and baseline data collection overview

Many of the NORIG participants will come from the Gastroparesis Registry (GpR) or from the patient rosters of the study physicians. Patients who appear to be eligible after chart review and completion of standard of care tests and procedures for gastroparesis will be invited to undergo screening for the NORIG trial. Patients considered by the clinical center investigator as likely to be eligible for participation in the NORIG trial may be consented, registered and screened at a visit that is part of the ongoing clinical care of the patient. Patients will be asked to consent for the collection, storage and use of DNA for genetic research, but may opt out of this component of the NORIG trial. Screening tests should be completed according to the standard of care as outlined in the Standard Operating Procedures IV: Standards of Care for Patients with Idiopathic Gastroparesis.

As part of the screening process for the NORIG trial, the gastroparesis patient must have a standardized 4 hour scintigraphic evaluation of gastric emptying using a low fat Egg Beaters meal that is available for review by the study physician as outlined in the Standard Operating Procedures, Part I, section 6.3. This may be repeated as part of standard of care for diagnosis or follow-up as determined by the clinical center investigator during screening. The standard of care gastric emptying scintigraphy may have been obtained at any time within 2 years prior to the registration date. Patients must also have a negative upper endoscopy within the last 2 years, to rule out other potential causes of symptoms such as mechanical obstruction, inflammatory or other structural lesions of the GI tract or non-gastrointestinal causes. Recording of screening data on trial forms may not start until the patient has signed the NORIG trial consent statement. Screening and baseline data collection procedures will include questionnaires, physical examination, various laboratory tests, clinical procedures on patients and review of the patient's medical chart. Data abstracted from a patient's chart may include laboratory, endoscopy, scintigraphy and radiology test results. Prior therapy for gastroparesis will be reviewed, and patients will be asked to stop specific treatments such as tricyclic antidepressants, monoamine oxidase inhibitors, strongly anticholinergic medications, calcium channel blockers, and erythromycin. Narcotic pain medication including fentanyl patches and other rescue medications such as propoxyphene or propoxyphene with acetaminophen may not be used more than 3 days per week.

All participants who sign the consent statement will be registered in the trial database. Each participant who starts screening will be accounted for at the end of screening, as either a screening success (randomization) or a screening failure. A screening failure is defined as a participant who signed the consent form and was registered in the NORIG trial data system, but is found to be ineligible prior to randomization; screening failures include patients who meet medical eligibility criteria but change their mind and do not consent to randomization into the trial. The reason for screening failure will be recorded on the randomization form and keyed in the trial database.

Screening and baseline data collection procedures will be conducted over two clinic visits completed on separate calendar days. The goal of the first screening visit is to obtain consent and start recording screening data regarding the trial's inclusion and exclusion criteria on NORIG data forms; the goal of the second screening visit is to complete collection of baseline data on patients who appear to be eligible. This separation of procedures between two visits is somewhat arbitrary and is provided as a guideline. Screening procedures and data collection can be organized as appropriate at each clinical center. The procedures completed during screening include:

- **Screening visit 1:** The patient should be in a fasting state (no food or drink after midnight the night before) for this visit. The patient will sign the consent at or prior to screening visit 1 and will undergo a history and physical examination to identify other illness and contraindications for participation such as use of narcotics for pain more than 3 days per week (including fentanyl patches), use of calcium channel blockers, use of erythromycin, use of medications that are strongly anticholinergic, hypersensitivity or allergy to any tricyclic antidepressant drug, concomitant therapy with a monoamine oxidase inhibitor (MAOI), recent myocardial infarction or glaucoma. The baseline medical history form will have a section to establish a baseline symptom profile for each participant and to document non-specific symptoms that may be attributed as side effects to study drug after randomization. The patient will be asked to respond to the clinical global patient impression (CGPI). Patients will complete the following questionnaires:

- Gastrointestinal Symptom Rating Scale (GSRS)
- Health-related quality of life questionnaire (SF-36)
- Beck Depression Inventory (BDI-II)
- Patient Assessment of Upper Gastrointestinal Disorders Symptom Severity (PAGI-SYM)
- State Trait Anxiety Inventory (STAI)
- Brief Pain Inventory (BPI)
- Patient Health Questionnaire (PHQ-15)

Anthropometric assessments (body weight [kg], body height [m], body mass index [BMI], waist circumference [cm], hip circumference [cm], vital signs (systolic and diastolic blood pressure, heart rate, respiratory rate, body temperature); and general physical findings will be collected and recorded. Patients will have an ECG performed at this visit. Laboratory test results that need to be recorded from chart review or obtained as part of screening visit 1 include: complete blood count (CBC): white blood cells, red blood cells, hemoglobin, platelets; a metabolic panel: sodium, potassium, chloride, carbon dioxide, calcium, magnesium, blood urea nitrogen (BUN), creatinine; a hepatic panel: albumin, total protein, alkaline phosphatase, alkaline aminotransferase (ALT), aspartate aminotransferase (AST), bilirubin; and thyroid stimulating hormone (TSH).

**Additional standard of care procedures required for screening:**

**Gastric emptying scintigraphy:** Patients who have not had a standardized 4 hour gastric emptying scintigraphy within 2 years of the registration date or whose previous gastric emptying scintigraphy is of inadequate quality must have a standard of care gastric emptying scintigraphy prior to randomization. Instructions for the gastric emptying scintigraphy are found in the Standard Operating Procedures I: Clinical Center Operations, section 6.3.

**Upper endoscopy:** Patients who have not had an upper endoscopy within 2 years of the registration date must have a standard of care upper endoscopy prior to randomization.

- **Screening visit 2:** Patients will return to the clinical center in a fasting state (no food or drink after midnight the night before). They will have blood drawn for plasma and DNA banking; 20 mL of the blood drawn will be used for DNA banking for future pharmacogenomic analysis of CYP450 2D6 alleles; and 10 mL will be used for plasma banking for future measurement of the study drug blood levels. Patients will undergo a satiety test with electrogastronomy (EGG).

**Electrogastronomy with satiety testing:** On the morning of the electrogastronomy (EGG) and satiety test, the patient will arrive fasting, that is, nothing to eat or drink after midnight the night before the test. Subjects may take normal medications with a small amount of water up to two hours prior to the study, but should refrain from coffee, tea, or juice. Electrogastronomy is the recording of the electrical activity of the smooth muscle in the stomach using electrodes similar to an electrocardiogram (ECG). EGG electrodes are placed on the abdominal skin. Skin preparation for these electrodes will consist of cleaning the skin with an electrode paste and then applying a conduction gel which is then wiped off. If needed, the abdominal surface where electrodes will be positioned is shaved. Patients will undergo a 15 minute baseline EGG recording.

Then, for the satiety test, subjects will drink Ensure® (1.1.kcal/ml) every 5 minutes until they feel completely full. This will be followed by another 30 minute EGG recording. The electrodes will then be removed. The satiety test will be analyzed by the amount of Ensure® consumed. The EGG will be analyzed for each of the fasting and post nutrient load 30 minute periods. The percentage distribution of the power in the normal frequency range (2.5-3.75 cycles per minute [cpm]), tachygastronomia (>3.75-10 cpm), bradygastronomia (<2.5 cpm) and duodenal-respiration (>10 cpm) will be calculated. A power ratio comparing mean signal amplitudes between postprandial and preprandial power will be calculated. The dominant frequency, and the percentage of time in the dominant frequency will be calculated and recorded. Data will be available in a digital format for further analysis. Detailed instructions for the electrogastronomy and satiety test are found in the SOP I, section 6.7.

The NORIG web based data system will include software to check patient eligibility based on keyed data forms. The eligibility check task may be run at any time, and there is no limit on the number of times it may be run before randomization. The output from the task will list the eligibility checks that the patient has failed and a summary finding that the patient is eligible or ineligible for

the trial. Clinical center staff can use this task to identify the items that still need to be completed, keyed, or verified after data from screening visits are keyed. The randomization visit should not take place until the eligibility check indicates that the patient is eligible except for the items that can be completed only at the randomization visit.

### 5.3 Randomization visit

Randomization is the act of generating the random study medication assignment from the web-based data management system and is the procedure which defines a patient's enrollment into the trial. Randomization can only occur after eligibility has been fully checked and all data collected at screening visits have been keyed to the trial database. The patient will re-affirm their consent and have their vital signs recorded. Women of child bearing potential must have a negative pregnancy test.

The final task at the randomization visit is the generation of the random treatment assignment. The generation process includes the same electronic check on eligibility that the staff may run prior to the randomization visit. The medication assignment will not be generated unless the check finds that the patient is eligible, and the clinic staff indicates that they want to randomize the patient.

The random treatment assignment will consist of a numbered medication bottle; this number will be unique as well as patient and visit specific. This will correspond to numbered bottles of medication which have been sent to the clinical center's research pharmacy (or clinical coordinator if not using a pharmacy) by the GpCRC Drug Distribution Center. The research pharmacy (or clinical coordinator) will issue the specific numbered bottle to the patient. Each patient's random treatment assignment will be generated for that specific patient and will not be transferable to another patient. Once the assignment has been generated, the patient should be issued the assigned study drug (in person) and instructed about when to take the study drug and monitoring for potential adverse effects. The study drug dispensed at the time of randomization will be either a 10 mg capsule of nortriptyline or a similar looking placebo capsule.

The date of randomization is the start (zero) time for reckoning all follow-up visits (i.e., all follow-up visits are scheduled at specific times measured from the date of randomization). The randomization computer program will generate a personalized appointment schedule for the patient; this schedule will indicate the target date for each follow-up visit, as well as the time window around the target date during which the follow-up visit may be done.

#### 5.4 Follow-up visits

Patients will return for follow-up visits at 3, 6, 9, 12, 15, and 18 weeks after randomization. Patients will be given a new, higher dosage of the study drug at each follow-up visit until week 9 as long as in the opinion of the investigator, there are no significant side effects attributed to the study drug. If there have been side effects, investigators can either reduce the dose to the previous well-tolerated dose; or in the case of significant side effects, may stop therapy for one week to monitor symptoms as outlined in section 5.7 safety issues. The specific procedures to be completed at each of the follow-up visits are:

- **Week 3 visit:** Medical history including side effect or symptom profile, global overall relief of symptoms question and clinical global patient impression question, and the following questionnaires should be completed: Patient Assessment of Upper Gastrointestinal Disorders Symptom Severity (PAGI-SYM), Gastrointestinal Symptoms Rating Scale (GSRS), and Beck Depression Inventory (BDI-II). Review study drug adherence and tolerance with the initial 10 mg dose of study drug with patient. Collect any remaining medication bottles with unused study drug. If 10 mg dose is well tolerated during the first 3 weeks after randomization, dispense study drug with instructions for a 25 mg dose.

- **Week 6 visit:** Medical history including side effect or symptom profile, global overall relief of symptoms question and clinical global patient impression question; and the following questionnaires should be completed: Patient Assessment of Upper Gastrointestinal Disorders Symptom Severity (PAGI-SYM), Gastrointestinal Symptoms Rating Scale (GSRS), and Beck Depression Inventory (BDI-II). Review study drug adherence and tolerance with the 25 mg dose of study drug since the week 3 visit with patient. Collect any remaining medication bottles with unused study drug. If 25 mg dose is well tolerated during weeks 3-6 after randomization, dispense study drug with instructions for a 50 mg dose (two 25 mg capsules).

- **Week 9 visit:** Medical history including side effect or symptom profile, global overall relief of symptoms question and clinical global patient impression question; physical exam (temperature, heart rate, respiratory rate, blood pressure); and the following questionnaires should be completed: Patient Assessment of Upper Gastrointestinal Disorders Symptom Severity (PAGI-SYM), Gastrointestinal Symptoms Rating Scale (GSRS), a health-related quality of life questionnaire (SF-36), State Trait Anxiety Inventory (STAI), Brief Pain Inventory (BPI), Patient Health Questionnaire (PHQ-15), and Beck Depression Inventory (BDI-II). Once the questionnaires are completed, the patient will have an electrocardiogram (ECG). Review ECG findings, study drug adherence and tolerance with the 50 mg dose of study drug since the week 6 visit with patient. Collect any remaining medication bottles with unused study drug. If 50 mg dose is well tolerated during weeks 6-9 after randomization, dispense study drug with instructions for a 75 mg dose (three 25 mg capsules). Women of childbearing potential must have a negative pregnancy test.

- **Week 12 visit:** Patient should be in a fasting state (no food or drink after midnight the night before). Medical history including side effect or symptom profile, global overall relief of symptoms question and clinical global patient impression question; physical exam (temperature, heart rate,

respiratory rate, blood pressure). They will have blood drawn for plasma banking and analysis; 10 mL of blood will be drawn for plasma banking; and 15 mL will be drawn for a complete blood count (white blood cells, red blood cells, hemoglobin, hematocrit, platelets), a metabolic panel (sodium, potassium, chloride, carbon dioxide, calcium, magnesium, blood urea nitrogen (BUN), creatinine, and a hepatic panel (albumin, total protein, alkaline phosphatase, alkaline aminotransferase (ALT), aspartate aminotransferase (AST), bilirubin. The following questionnaires should be completed: Patient Assessment of Upper Gastrointestinal Disorders Symptom Severity (PAGI-SYM), Gastrointestinal Symptom Rating Scale (GSRS), and Beck Depression Inventory (BDI-II). Once the questionnaires are completed, the patient will have an electrocardiogram (ECG) followed by the EGG and satiety test. For the EGG and satiety test, patients will have a 15 minute baseline EGG recording. Then the patient will drink Ensure® (1.1.kcal/ml) every 5 minutes until they feel completely full. This will be followed by a 30 minute EGG recording. The electrodes will then be removed. The satiety test will be analyzed by the amount of Ensure® consumed. The EGG will be analyzed for the fasting and post satiety test. Review ECG findings, study drug adherence and tolerance with the 75 mg dose of study drug since the week 9 visit with patient. Collect any remaining medication bottles with unused study drug. If 75 mg dose is well tolerated during weeks 9-12 after randomization, dispense study drug with instructions for a 75 mg dose (three 25 mg capsules). Women of childbearing potential must have a negative pregnancy test.

- **Week 15 visit:** Patient should be in a fasting state (no food or drink after midnight the night before). Medical history including side effect or symptom profile, global overall relief of symptoms question and clinical global patient impression question, physical exam (temperature, heart rate, respiratory rate, blood pressure); 10 mL of blood will be drawn for plasma banking, and the following questionnaires should be completed: Patient Assessment of Upper Gastrointestinal Disorders Symptom Severity (PAGI-SYM), Gastrointestinal Symptom Rating Scale (GSRS), a health-related quality of life questionnaire (SF-36), State Trait Anxiety Inventory (STAI), Brief Pain Inventory (BPI), Patient Health Questionnaire (PHQ-15), and Beck Depression Inventory (BDI-II). Review laboratory results, study drug adherence and tolerance with the 75 mg dose of study drug since the week 12 visit with patient. Collect any remaining medication bottles with unused study drug. Patients will be instructed to reduce their dosage to 50 mg (two 25 mg capsules) for one week and then to 25 mg (one capsule) the second week and end with one week of no study drug use and return for the final follow-up visit at week 18. Women of childbearing potential must have a negative pregnancy test.

- **Week 18 visit:** Medical history including side effect or symptom profile, global overall relief of symptoms question and clinical global patient impression question, and the following questionnaires should be completed: Patient Assessment of Upper Gastrointestinal Disorders Symptom Severity (PAGI-SYM), Gastrointestinal Symptom Rating Scale (GSRS), and Beck Depression Inventory (BDI-II). Collect any remaining medication bottles with unused study drug.

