### 3.2 Treatment groups

Patients who have signed an informed consent statement and who meet the eligibility criteria will be randomly assigned to one of two groups for 15 weeks of treatment followed by a 3 week tapering period where the dose is decreased by 25 mg (one capsule) each week until week 17, then no study drug is taken for the last week of the trial:

- Group 1:** Nortriptyline; 10 mg, one capsule, po qhs (by mouth at bedtime each night) x 3 weeks,  
f03 visit, 25 mg, one capsule, po qhs x 3 weeks,  
f06 visit, 50 mg, two capsules, po qhs x 3 weeks,  
f09 visit, 75 mg, three capsules, po qhs x 6 weeks,  
f15 visit: taper study drug by one capsule a week, off study drug for the last week
- Group 2:** Nortriptyline-placebo; 10 mg, one capsule, po qhs x 3 weeks,  
f03 visit, 25 mg, one capsule, po qhs x 3 weeks;  
f06 visit, 50 mg, two capsules, po qhs x 3 weeks;  
f09 visit, 75 mg, three capsules, po qhs x 6 weeks  
f15 visit: taper study drug by one capsule a week, off study drug for the last week

The randomization scheme will assign patients in randomly permuted blocks of assignments stratified by clinical center; block size will be determined randomly. This scheme will ensure that the two groups will be balanced by calendar time of enrollment (to minimize secular effects) and by clinical center (to minimize clinic-specific effects of differences in patient populations and management).

The randomization plan will be prepared and administered centrally by the Data Coordinating Center (DCC) but will not require real time interaction with a DCC staff member. Requests for randomizations will be made by the clinical center using a web-based application. An assignment will be issued only if the database shows that the patient is eligible, has signed the consent statement, and has had all required baseline data keyed to the data system.

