### 3.3 Study drug dosing schedule

Study drugs will be shipped to each clinical center's investigational drug pharmacy. The research pharmacy staff will then provide the investigator with masked study drug medication bottles based on the DCC randomization schedule. Patients will be dispensed one or more bottles labeled *“nortriptyline or placebo”*.

Each evening, 30 minutes before bedtime, one or more capsules from the “nortriptyline or placebo” bottle will be taken with water. Study drug may be taken with food. The study drug will be either a dose of nortriptyline or matching placebo. Patients will be on a dose escalation regimen with an initial dose of one 10 mg capsule the first three weeks after randomization. At the week 3 visit, study drug dose will be increased to one 25 mg capsule for the next 3 weeks, if well tolerated. At the week 6 visit, study drug dose will be increased to 50 mg (two 25 mg capsules) for the next 3 weeks, if well tolerated. At the week 9 visit, a follow-up electrocardiogram (ECG) will be performed, the ECG findings will be reviewed and if well tolerated, the study drug dose will be increased to 75 mg (three 25 mg capsules) for the remaining 6 weeks until 15 weeks after randomization. At the week 12 visit, patients will have a second follow-up ECG and a blood draw for a complete blood count, metabolic and hepatic panel, and if well tolerated, the study drug dose will remain the same at 75 mg (three 25 mg capsules) for the remaining 3 weeks of treatment phase of NORIG trial. At the week 15 visit, patients will be instructed to taper the study drug, decreasing the dose to 50 mg (two 25 mg capsules) for one week, at week 16, decreasing to 25 mg (one 25 mg capsule) for one week, and starting with week 17, the study drug will be discontinued, i.e., no study drug will be taken for the final week.

At each follow-up visit, patients should return their medication bottles with any study drug not taken. The pharmacist or clinical coordinator should count and record the remaining capsules in study drug bottles on the NORIG data form.

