### 3.4 Restarts and dose adjustments due to side effects

A standardized management plan for potential side effects and symptoms is detailed in section 5.7 Safety issues. If a common, non-serious side effect to the study drug develops which is noticeable but tolerable, investigators will follow a standardized management plan as outlined in section 5.7 of the protocol. These side effects include ones commonly seen with TCAs such as constipation, dry mouth, weight gain, bloating, dizziness, insomnia. The management plan for these common, non-serious side effects generally involves patient education about the side effect and adding over the counter therapies. The study drug is continued with dose escalation. If the side effect becomes bothersome and barely tolerable, then the study drug dosage is reduced to the last dose tolerated without stopping treatment. If the side effect is intolerable, then the study drug is discontinued for one week and then restarted at the lower dosage that was previously tolerated.

If side effects occur that may be more serious, such as heart palpitations, skin rash, anxiety, confusional states, panic, then the patient will be evaluated. For heart palpitations, an ECG will be

obtained. Investigators can initially attempt dose reduction to the previous well tolerated dose instead of treatment interruption. If patients developed serious or intolerable side effects requiring cessation of study drug, the drug will be stopped for one week. If the side effects disappear, a second attempt will be made to reintroduce the study drug after one week at the previous lower dose that the participant tolerated better. If the dose is well tolerated, the patient will be continued at this dose for the remainder of the study without further dose escalation. If the study medication is stopped, the patient will no longer receive the study drug, but will be followed in the study according to the protocol, in keeping with the "intention-to treat" paradigm.

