## 9.2 Data collection schedule

Assessment/Procedure	Screening Visits			Follow-up visits Weeks from randomization					
	s1	s2	rz	3	6	9	12	15	18
Consent	X	.	.	.	.	.	.	.	.
Gastric emptying scintigraphy review	X	.	.	.	.	.	.	.	.
Upper endoscopy review	X	.	.	.	.	.	.	.	.
Baseline medical history	X	.	.	.	.	.	.	.	.
PAGI-SYM questionnaire	X	.	.	X	X	X	X	X	X
GSRS questionnaire	X	.	.	X	X	X	X	X	X
SF-36 QOL questionnaire	X	.	.	.	.	X	.	X	.
Beck Depression Inventory-II	X	.	.	X	X	X	X	X	X
State Trait Anxiety Inventory	X	.	.	.	.	X	.	X	.
Brief Pain Inventory	X	.	.	.	.	X	.	X	.
PHQ-15 questionnaire	X	.	.	.	.	X	.	X	.
Electrocardiogram (ECG)	X	.	.	.	.	X	X	.	.
Physical exam	X	.	X	.	.	X	X	X	.
Satiety test with electrogastrography (EGG)	.	X	.	.	.	.	X	.	.
Study drug dispensed	.	.	X	X	X	X	X	.	.
Review of study drug adherence	.	.	.	X	X	X	X	X	X
Follow-up medical history including review of adverse events	.	.	.	X	X	X	X	X	X
Labs	.	.	.	.	.	.	.	.	.
CBC, metabolic and hepatic panel	X	.	.	.	.	.	X	.	.
TSH	X	.	.	.	.	.	.	.	.
Plasma banking	.	X	.	.	.	.	X	X	.
DNA banking	.	X	.	.	.	.	.	.	.
Pregnancy test	X	.	X	.	.	X	X	X	.

**Physical exam:** includes measurement of weight, height, waist and hip circumferences, vital signs (temperature, heart rate, blood pressure) general physical findings

**CBC:** Complete blood count: white blood cell count, red blood cell count, hemoglobin, hematocrit, platelet count

**Metabolic panel:** sodium, potassium, chloride, carbon dioxide, glucose, calcium, magnesium, blood urea nitrogen (BUN), creatinine.

**Hepatic Panel:** albumin, total protein, bilirubin, alkaline phosphatase, alkaline aminotransferase (ALT), aspartate aminotransferase (AST)

**TSH:** Thyroid Stimulating Hormone

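### The week 15 taper is written as fixed doses that fit only a patient on 75 mg, conflicts with the one-capsule-a-week rule stated elsewhere, and has no scheduled supply

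*Protocol*

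**What the plan says.** The protocol describes the taper after week 15 in two ways.

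- **Fixed doses.** Section 5.4 (Week 15 visit) states "Patients will be instructed to reduce their dosage to 50 mg (two 25 mg capsules) for one week"; a second week at 25 mg and a final week off drug follow. Section 3.3 has the same sequence: "decreasing the dose to 50 mg (two 25 mg capsules) for one week, at week 16, decreasing to 25 mg (one 25 mg capsule". Neither makes the sequence depend on the dose the patient is taking.
- **A relative step.** Section 3.2 describes a "tapering period where the dose is decreased by 25 mg (one capsule) each week until week 17". Section 3.1 also gives 25 mg per week, and the synopsis gives one capsule per week.

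The protocol expects some patients to be below 75 mg at week 15. For a patient restarted at a lower dose, section 3.4 says "the patient will be continued at this dose for the remainder of the study without further dose escalation". Section 5.7 holds the reduced dose to the end of the study for several side effects, including dizziness, drowsiness, tremor and fatigue. Both sections also describe patients who stop drug and remain in follow-up.

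On supply, the week 15 text says "Collect any remaining medication bottles with unused study drug" and gives no dispensing instruction. In Appendix 9.2 the row "Study drug dispensed" is marked at randomization and at weeks 3, 6, 9 and 12, but not at week 15.

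**The concern.** The patients for whom the two versions differ are those already known not to tolerate higher doses. A site following the week 15 text has no usable instruction for them, and a site following section 3.2 reaches a different answer. Under Appendix 9.2 the last scheduled ECG and safety laboratory tests are at week 12, and no visit falls between weeks 15 and 18, so a misapplied taper would meet no scheduled check.

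The supply gap concerns every patient still on drug at week 15. Section 3.1 says that the taper is there to limit withdrawal symptoms. If a site dispensed nothing, patients on nortriptyline would stop abruptly while placebo patients would have no active drug to withdraw from. Any resulting difference would appear in the week 18 symptom and side-effect data. It would also enter the sensitivity analysis in section 6.2 that averages GCSI over all follow-up visits, if that average includes week 18.

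**Working it through.** **1. The fixed sequence reproduced from 75 mg.** Lowering 75 mg by 25 mg a week gives 75 − 25 = 50, 50 − 25 = 25 and 25 − 25 = 0. This is the 50/25/0 sequence of sections 3.3 and 5.4, so the two versions agree at the nominal dose.

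**2. The same comparison for every dose a patient may hold at week 15.** The doses come from sections 3.3, 3.4 and 5.7. The first-step change under the fixed text is 50 minus the current dose.

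| Dose at week 15 (mg) | Fixed text (3.3, 5.4) | First-step change (mg) | One capsule less per week (synopsis, 3.2) |
|---|---|---|---|
| 75 | 50 / 25 / 0 | −25 | 50 / 25 / 0 |
| 50 | 50 / 25 / 0 | 0 | 25 / 0 / 0 |
| 25 | 50 / 25 / 0 | +25 | 0 |
| 10 | 50 / 25 / 0 | +40 | 0 |
| Off drug | 50 / 25 / 0 | +50 | 0 |

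The versions match only in the first row. Taken literally, the fixed first step is 50/50 = 1, 50/25 = 2 and 50/10 = 5 times the dose of patients held at 50, 25 and 10 mg, and it reads as a restart for those off drug.

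**3. The relative rule at 10 mg.** Section 3.2 equates one capsule with 25 mg. The starting capsule is 10 mg, and 10 − 25 = −15 is not a dose. One capsule fewer gives zero, so the capsule wording works at 10 mg but the milligram wording does not.

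**4. Supply.** The fixed taper needs 2 × 7 + 1 × 7 = 21 capsules of 25 mg after week 15. The week 12 text dispenses drug with instructions for 75 mg, which for the three weeks to week 15 is 3 × 21 = 63 capsules, and it mentions no taper supply. At weeks 3, 6, 9 and 12 the collection of bottles is followed by a dispensing step; at week 15 it is not. The week 18 text again collects unused drug, and Appendix 9.2 marks an adherence review at that visit, so the protocol assumes that patients hold drug after week 15. It does not say where that drug comes from.

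**5. Reach.** The primary outcome in section 6.2 is confined to the 15 weeks of treatment. Neither it nor the sample size depends on the taper.

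**The case against.** The best defence is that sections 3.3 and 5.4 describe the nominal course. Section 3.3 has the patient remaining at 75 mg if that is tolerated just before it gives the taper, and section 5.4 reviews tolerance of 75 mg first. Both use verbs that mean lowering the dose, which cannot describe going from 10 or 25 mg to 50 mg. On this view, 50 then 25 mg is the one-capsule rule worked out from 75 mg, and the rule in the synopsis and sections 3.1 and 3.2 governs everyone else. Section 3.4 also bars further escalation after a restart.

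Much of this stands. A reader might infer that the protocol orders a dose increase for patients who could not tolerate more. The documents do not support that: the wording and the relative rule both show that no increase was intended, and the twofold and fivefold ratios come only from a literal reading of two sections. What remains is that these sections fail for patients below 75 mg and do not say which other rule then applies.

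On supply, a reader might infer that all patients stop abruptly at week 15. That is not shown either. Bottle quantities are not given, the week 12 supply might have been meant to cover the taper, and the collection sentence appears at every follow-up visit. Even so, nothing says that collected bottles are handed back, and neither the visit text nor the schedule provides for dispensing.

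It is also fair to say that, by design, every patient is off drug for the week before the week 18 visit. That limits the effect on week 18 data but does not remove it.

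**Conclusion.** The contradiction holds. The fixed and relative tapers agree only from 75 mg, and neither is written explicitly for patients who reach week 15 below that dose or off drug. The supply gap also holds as an inconsistency: drug is to be taken for two weeks after a visit at which bottles are collected and no dispensing is scheduled. Abrupt withdrawal is a possible consequence, not a demonstrated one.

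The size cannot be stated in patients, because the protocol gives no expected number below 75 mg. The consequences are for patient safety, consistent conduct across sites and the week 18 data, including the average over follow-up visits if week 18 is counted. The primary outcome and the power are untouched. The correction is warranted because the text concerns dosing of patients with known intolerance and is cheap to repair.

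**What to change.** Reconcile sections 3.1 to 3.4, 5.4 and 5.7, together with the synopsis, so that one taper instruction explicitly covers patients who reach week 15 below 75 mg, including those on the 10 mg capsule, and those already off drug. Reconcile the week 15 text with the dispensing row of Appendix 9.2 so that the source of taper supply is stated in the same way in both places. Which taper and which doses apply is for the clinical team to decide.

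The cost is protocol wording and one cell of the schedule, and possibly one more masked bottle at week 15.
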